## 1. TERMS, ACRONYMS, ABREVIATIONS

---

The following abbreviations and specialist terms are used in this protocol.

AE	Adverse event
APT	Acoustic Pulse Thrombolysis
aPTT	Activated partial thromboplastin time
BNP	Brain natriuretic peptide
CE	European Conformity
CFR	Code of Federal Regulation
CRA	Clinical research associate
CTA	Computed tomography angiography
CTEPH	Chronic thromboembolic pulmonary hypertension
CV	Curriculum vitae
DM	Data management
DMP	Data management plan
DVT	Deep vein thrombosis
eCRF	Electronic case report form
EDC	Electronic data capture
EP	Efficacy population
ePRO	Electronic Patient Reported Outcomes
EQ-5D-5L	Euroqol five dimension five level questionnaire
FDA	Food and Drug Administration
FPI	Full prescribing information
GCP	Good clinical practice
Hct	Hematocrit
Hgb	Hemoglobin
HIPAA	Health Information Portability and Accountability Act
ICF	Informed consent form
ICH	Intracranial hemorrhage
ICU	Intensive care unit
ID	Identification
IDDC	Intelligent Drug Delivery Catheter
IFU	Instructions for Use
INR	International normalized ratio
IP	Investigational product
IRB/EC	Institutional review board/ethics committee
IVC	Inferior vena cava
LV	Left ventricular
MHz	Megahertz
MSD	MicroSonic device
PE	Pulmonary embolism
PEmb-QOL	Pulmonary Embolism Quality of Life
PHI	Protected health information
PT	Partial thromboplastin time
Pts	Patients
QOL	Quality of Life
r-tPA	Recombinant tissue plasminogen activator

RV	Right ventricular
RVSP	Right ventricular systolic pressure
SAE	Serious adverse event
SAP	Statistical analysis plan
SoC	Standard of care
SP	Safety population
sPESI	Simplified pulmonary embolism severity index
SpO 2	Peripheral capillary oxygen saturation
SvO 2	Mixed venous oxygen saturation
TAPSE	Tricuspid annular plane systolic excursion
U.K.	United Kingdom
U.S.	United States
VTE	Venous thromboembolism

## 2. PROTOCOL SYNOPSIS

Protocol Number	BTG-001163-01
Protocol Short Title	KNOCOUT PE
Protocol Title	Retrospective and prospective international EKoSOnic® registry study Of the treatment and Clinical OUTcomes of patients with Pulmonary Embolism
Intervention	
Device: EkoSonic® Endovascular System (EKOS) employs high frequency (2-3 MHz), low power ultrasound to facilitate the delivery of physician-specified fluids, including thrombolytics, in the pulmonary arteries.
 
Acoustic Pulse Thrombolysis (APT) Procedure: The clinical use of the EKOS device in combination with physician-specified fluids.

Type of Protocol	International Registry
Trial Objectives	

• To understand the APT treatment protocol used as SoC across institutions and document changes in practice following the OPTALYSE PE study results

• To describe the effects of varied APT protocols on long-term patient outcomes

Outcome Measures	

1. Change in the ratio of the measurement of the right ventricular to left ventricular diameters (RV/LV) as measured on echocardiogram or computed tomography angiography (CTA) from baseline to between 24 – 48 hours (hr) after the start of the APT procedure (matched pairs as available).

2. Diagnosis of pulmonary hypertension defined as mean pulmonary artery pressure greater than 25mm Hg by echocardiogram that persists at least 3 months after PE diagnosis

3. Frequency and safety outcomes of adjunctive therapies post APT procedure during hospitalization

4. Number of patients with non or partial response to other interventional procedures prior to APT procedure for index PE

5. Frequency and severity of serious adverse experiences (SAE) related to EKOS or procedure, major bleeding, or venous thromboembolic disease (VTE) during index hospitalization and during first 12 months post-APT procedure

6. All-cause mortality during first 12 months post-APT procedure

7. Recurrent symptomatic PE, PE related death, hemodynamic collapse at 30 days (composite measure)

8. Healthcare utilization during hospitalization:

a. Time from hospital admission to ICU discharge

b. Time from hospital admission to discharge

	
9. Quality of life (QOL) as measured by the Pulmonary Embolism Quality of Life (PEmb-QOL) and EuroQol five dimension five level questionnaire (EQ-5D-5L) at 3 month and 12 month post-hospitalization follow-up visits
 
10. IVC filter placement (measured by number of occurrences)

	
RETROSPECTIVE
 
Data collection is expected to occur over a 6 month period at each site

Trial Duration	
PROSPECTIVE
 
Enrollment will take place over approximately a 24 month period. For each subject, their participation in the registry lasts 12 months.

Trial Design	
A multi-center retrospective and prospective registry of the APT treatment of patients (pts) with submassive (Intermediate-High Risk) and massive (High Risk) PE. The retrospective portion of the registry will consist of consecutive patients treated with APT between January 1, 2014 and one year prior to date of site activation. The prospective portion of the registry will collect data for pts diagnosed and risk-stratified and treated with APT procedure. Pts will be followed for 12 months.

	
Intermediate-High Risk PE will be defined by evidence of RV dysfunction (<math>RV/LV \geq 1.0</math>), hemodynamic stability (normal systemic arterial blood pressure <math>>90</math> mmHg), and troponin elevation.
 
High Risk PE will be defined with hemodynamic instability (normal systemic arterial blood pressure <math><90</math> mm Hg and/or use of vasopressors)

Number of Patients	
RETROSPECTIVE
 
Up to 1000 evaluable cases

	
PROSPECTIVE
 
Up to 550 consented patients to yield 500 evaluable patients

Number & Location of Sites	
Up to 100 sites geographically distributed throughout North America, Europe, and Asia

Eligibility Criteria	
RETROSPECTIVE
 
Inclusion Criteria
 

1. Treated with APT procedure between January 1, 2014 and one year prior to date of site activation

2. <math>RV/LV \geq 1.0</math> from diagnostic CTA or echocardiogram

3. PE symptom duration <math>\leq 14</math> days

	
4. Troponin elevation
 
Exclusion Criteria
 
5. Enrollment into the OPTALYSE PE study

PROSPECTIVE	
Inclusion Criteria
 
1. Male or female <math>\geq</math> 18 years of age and <math>\leq</math> 80 years of age
 
2. RV/LV <math>\geq</math> 1.0 from diagnostic CTA or echocardiogram
 
3. PE symptom duration <math>\leq</math> 14 days
 
4. Troponin elevation
 
5. Signed informed consent obtained from subject or legally authorized representative
 
6. Investigator has selected EKOS to treat patient with massive or submassive PE
 
Exclusion Criteria
 
7. Clinician deems the subject high-risk for catastrophic bleeding
 
8. Life expectancy < one year

Sample Size Justification	The aim of the registry is to collect observational data on standard of care APT treatment. The sample size is calculated from the expected enrollment per site based on estimated cases per physician across total number of sites. For retrospective cases, up to 1000 cases will be collected to capture details of PE treatment with EKOS from the time it became commercially available to the time the site was activated. For prospective, up to 500 patients will be treated to collect data on current EKOS use at up to 100 sites.
Statistical Methods	
Patients will be analyzed according to the APT treatment protocol they received (i.e. duration of treatment and dose, type of fluid received). Frequency of use of each of the APT treatment protocols before and after OPTALYSE PE results were made public will be summarized and compared using fisher's exact test.
 
Each outcome measure will be summarized for the full registry population as well as separately by the different APT treatment protocols, including 95% confidence intervals. Additionally, outcome measures will be summarized by the following subgroups: submassive and massive PE, each region, and by the retrospective and prospective portions of the registry.

Registry Procedures	See section 3. SCHEDULE OF REGISTRY ASSESSMENTS – PROSPECTIVE below

Registry Follow-up Visits	For prospective subjects, patients should be followed per Investigator's standard of care (SoC). Data will be collected for any echocardiograms and CTAs completed throughout the 12 month follow-up period. At minimum, a health status check should be performed at 3 and 12 months. An on-site visit with echocardiogram is recommended at 3 months for patients with abnormal echocardiogram post-treatment for evaluation of chronic pulmonary hypertension, and at 12 months for all patients. Safety data should be reported through 12 months post-index procedure. For retrospective cases, long term health data will be collected as available for up to 12 months post-index treatment.
Treatment	Subjects scheduled for treatment with EKOS will be treated as prescribed by the Investigator SoC for treating PE and in accordance with the instructions for use (IFU).  Post-procedure care should be performed and prescribed in accordance with Investigator's SoC and as specified in the protocol.
Data Collection	All data will be collected via an electronic data capture (EDC) system. The Investigator and Investigator's staff will enter registry data into the EDC through a web portal. Each Investigator and Investigator staff member is granted a unique login into the EDC platform.

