## **8. MEASUREMENTS – RETROSPECTIVE**

### **8.1 Screening/Baseline**

The following data will be collected for screening, as available. Record most recent assessments prior to beginning of APT procedure.

- Review and confirmation of eligibility to participate in the registry
- Demographic information, medical history, and clinical risk factors
- CTA to evaluate the anatomic location of PE and degree of RV enlargement (as part of the initial diagnosis of PE). The RV/LV ratio at end-diastole will be determined from this image.
- Echocardiogram to measure: RV/LV ratio, TAPSE, estimated RVSP, and the collapse of the IVC with respiration
- Laboratory tests
  - Hemoglobin (Hgb)
  - Hematocrit (Hct)
  - Platelet count
  - Bleeding Times: aPTT, PT, and INR
  - Biomarker measurements: Troponin (to confirm eligibility), BNP/NT-proBNP, lactate/lactic acid, and D-dimer
- Anticoagulation medications 72 hours leading up to the APT procedure

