### **8.3 Post-Procedure**

---

The following data will be collected as available:

- First set of vital signs after end of APT procedure
- Laboratory tests
  - Hemoglobin (Hgb)
  - Hematocrit (Hct)
  - Platelet count
  - Creatinine
  - Bleeding Times: aPTT, PT, and INR
  - Biomarker measurements: Troponin, BNP/NT-proBNP, lactate/lactic acid, and D-dimer
- Echocardiogram 24 – 48 hours after start of APT procedure: RV/LV ratio, TAPSE, estimated RVSP, and the collapse of the IVC with respiration
- CTA 24 – 48 hours after start of APT procedure: RV/LV ratio
- Vital signs once at same time each day of hospitalization through discharge
- Length of post-procedure hospitalization (date and time of hospital discharge)
- SAEs related to EKOS or procedure, bleeding events, or VTE events

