### **13.8 Additional Outcome Analyses**

Descriptive statistics will be used to summarize additional outcome assessments including:

- Healthcare utilization during hospitalization will be summarized for time from hospital admission to ICU and time from hospital admission to discharge.
- Quality of life (QOL) measures PEmb-QOL and EQ-5D-5L will be summarized by time point and /or study visit including change from baseline for continuous endpoints and shift tables for categorical endpoints.
- Frequency and outcomes of adjunctive therapies post APT procedure during hospitalization
- Number of patients with non or partial response to other interventional procedures prior to APT procedure for index PE
- IVC filter placement (measured by number of occurrences)

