#### 2.6 Additional outcome measures

Analyses of additional outcome measures will be performed for both the SP and EP populations. In addition to the analyses described below, additional outcome measures will also be summarized by the subgroups described in section 2.2.1. All observed data will be summarized without imputation for missing values.

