#### 2.6.1 Healthcare Utilization

Time from hospital admission to ICU and time from hospital admission to discharge will be summarized using descriptive statistics.

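### Outcome 8 counts stay from hospital admission but is reported by APT dose band, so days before APT add noise, and possibly bias, to the regimen-level figures

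*Protocol*

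**What the plan says.** The two parts of outcome 8 (Protocol synopsis and 5.3) are "Time from hospital admission to ICU discharge" and "Time from hospital admission to discharge". The analysis text keeps the same starting point. Protocol 13.8 has "time from hospital admission to ICU and time from hospital admission to discharge", and SAP 2.6.1 has "Time from hospital admission to ICU and time from hospital admission to discharge will be summarized using descriptive statistics". In both of these the ICU item has lost the word for discharge.

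The results are broken down by regimen. Protocol 13.1 promises every outcome separately for each APT treatment protocol, with 95% confidence intervals. SAP 2.6, which contains healthcare utilization, says that "additional outcome measures will also be summarized by the subgroups described in section 2.2.1". Those subgroups are five dose bands, submassive or massive PE, region, and retrospective or prospective portion.

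On time before APT, Protocol 6.2 limits PE symptom duration to 14 days. It sets no limit on hospital days before APT and does not exclude PE that arises in hospital. Outcome 4 counts patients whose response to another interventional procedure for the index PE was absent or partial before APT. Protocol 8.3 lists post-procedure length of stay as a retrospective data item, but no planned summary uses it. No planned summary starts stay at APT or reports the interval from admission to APT.

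**The concern.** A regimen can change what happens after it starts. It cannot change how long the patient had already been in hospital. A patient admitted for another illness who develops PE there, or one first treated by another procedure, brings those earlier days into the stay figure of whichever dose band they later fall in. If such patients are spread unevenly over the bands, the table shows a difference in stay that precedes APT. If they are spread evenly, the pre-APT days still widen the intervals.

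This matters because the stay table is where a reader will look for a regimen difference. Protocol 4.3 says that lower dose and shorter treatment appear to reduce costs tied to ICU and hospital stay. The clock also departs from the plan's usual convention: outcome 1 is timed from the start of APT, and the 12-month windows of outcomes 5 and 6 run from the APT procedure.

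**Working it through.** **No figure to reproduce.** The documents state no expected stay, standard deviation, effect size or power for outcome 8. The sample size rests on expected enrollment. What follows is an illustration with labelled assumptions.

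**1. Decomposition.** Stay from admission = (admission to APT) + (APT to discharge). Between two dose bands, the difference in mean stay is therefore the difference in mean post-APT time plus the difference in mean pre-APT time. Only the first term can be a regimen effect.

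**2. A scale for comparison.** Protocol 4.3 gives an average infusion of 18 h in earlier use and trial regimens of 2, 4 and 6 h.

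- 18 h against 2 h: 16/24 = 0.67 day
- 18 h against 6 h: 12/24 = 0.50 day
- 6 h against 2 h: 4/24 = 0.17 day

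These are differences in infusion time, not estimates of the effect on stay.

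**3. Size of the pre-APT term.** Spurious difference = (difference between bands in the share of patients with a long pre-APT stay) × (their extra pre-APT days). Both inputs are assumed. Results are in days.

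| Share difference | 3 extra days | 5 extra days | 7 extra days |
|---|---|---|---|
| 5 points | 0.15 | 0.25 | 0.35 |
| 10 points | 0.30 | 0.50 | 0.70 |
| 20 points | 0.60 | 1.00 | 1.40 |

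Against 0.67 day, the range runs from 23% (0.15/0.67) to 210% (1.40/0.67). Against 0.17 day, 5 points × 5 days (0.25) is already larger, while 5 points × 3 days (0.15) is not.

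**4. Noise when the bands are balanced.** If pre- and post-APT times are independent, total SD = √(SD_post² + SD_pre²), and the sample size needed for equal precision grows by (SD_post² + SD_pre²)/SD_post². Assumed values:

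- Equal bands of (1000 + 500)/5 = 300 patients, and a true difference of 0.67 day.
- SD_post of 3 or 5 days.
- SD_pre of 1.1, 2.6 or 4.1 days. These come from mixtures in which 10%, 20% or 30% of patients have a long pre-APT stay (mean 3, 5 or 7 days; SD 2, 4 or 5) and the rest have mean 0.5 and SD 0.5. For the first mixture the mean is 0.1×3 + 0.9×0.5 = 0.75, the variance is 0.1×(4+9) + 0.9×(0.25+0.25) − 0.75² = 1.19, and the SD is 1.1.

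Power is two-sided at 0.05 and serves only as a yardstick for precision, since no test of stay is planned.

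| SD_post | SD_pre | Sample-size factor | Power from APT start | Power from admission |
|---|---|---|---|---|
| 3 | 1.1 | 1.13 | 0.78 | 0.73 |
| 3 | 2.6 | 1.74 | 0.78 | 0.54 |
| 3 | 4.1 | 2.84 | 0.78 | 0.37 |
| 5 | 1.1 | 1.05 | 0.37 | 0.36 |
| 5 | 2.6 | 1.27 | 0.37 | 0.31 |
| 5 | 4.1 | 1.66 | 0.37 | 0.24 |

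The loss ranges from negligible to large, depending on an SD_pre that the documents do not give. A larger registry narrows the intervals but leaves the step 3 bias unchanged.

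**The case against.** The best defence is that outcome 8 is labelled healthcare utilization, and total stay from admission is a proper measure of that. It is summarized descriptively. The only test planned is Fisher's exact test on how often each APT protocol is used. All of this stands.

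Several stronger readings are tempting, and the documents do not support them:

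- **That stay by regimen serves the second objective.** That objective concerns long-term patient outcomes, and index-hospital stay is not one. The remark in Protocol 4.3 about costs is background from earlier trials.
- **That the plan expects long waits before APT.** The item "Anticoagulation medications 72 hours leading up to the APT procedure" (Protocol 8.1) and the 48-hour baseline window (10.1) are look-back periods for data. The in-hospital VTE figure in 4.1 is general epidemiology. Only outcome 4 points to earlier treatment, and it gives no share or duration.
- **That pre-APT days must swamp the regimen effect.** Infusion hours do not cap that effect, because 4.3 also links regimen to bleeding, which could change stay. Nor do they map onto the SAP bands, which are by dose: 8 mg/2 h, 8 mg/4 h and 12 mg/6 h all fall in the 4-12 mg band.

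Two further points count in the plan's favour. Prior procedures (SAP 2.6.3) are themselves summarized by dose band, so that imbalance would be visible, although the days it adds would not. And patients with in-hospital or previously treated PE may also stay longer after APT because of the same illness, which a later clock start does not correct.

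**Conclusion.** The point holds as a cheap improvement to a descriptive secondary summary. The admission-based measure is not itself an error. What is missing is a measure suited to the breakdown by regimen: pre-APT days cannot be caused by the regimen, are not limited by the eligibility criteria, and are neither reported nor removed. With balanced bands the consequence is noise only. With unequal bands it is bias, under the assumptions above 0.15 to 1.4 days against infusion-time contrasts of 0.17 to 0.67 day. Whether pre-APT time reaches the size of a real regimen effect cannot be settled from the documents, which give neither quantity.

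Separately, the ICU item is inconsistent. Read literally, Protocol 13.8 and SAP 2.6.1 measure time to reaching the ICU, whereas the synopsis and 5.3 measure time to leaving it.

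**What to change.** 1. Keep both admission-based times, labelled as total healthcare utilization.
2. In outcome 8 (synopsis and 5.3), Protocol 13.8 and SAP 2.6.1, add time from start of APT to ICU discharge and time from start of APT to hospital discharge. Use these in the dose-band and other subgroup tables.
3. In SAP 2.3.2, report admission-to-APT time by dose band as a baseline characteristic.
4. State in SAP 2.6.1 that the APT-start measures remove pre-APT days but not confounding by comorbidity.
5. In the same edit, make the ICU wording in Protocol 13.8 and SAP 2.6.1 agree with the synopsis and 5.3.

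The cost is SAP and protocol wording and a few table columns. The 24-48 hour imaging window already needs the APT start time, and outcome 8 already needs the discharge times. Protocol 10.3 could name ICU and hospital discharge date and time explicitly for prospective subjects.

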### 3. SCHEDULE OF REGISTRY ASSESSMENTS – PROSPECTIVE

Assessments will be performed per Investigator's SoC and collected according to the schedule below. Assessments marked with an asterisk (\*) pertain to an outcome measure or eligibility.

Assessment	Baseline	Procedure/Post Procedure	Follow-up	
	Day -1	Day 0 thru Discharge	3 Months (±14 Days) Post APT (Phone or Visit)	12 Months (±1 Month) Post APT (Phone or Visit)
Informed Consent	X*			
Demographics	X*			
Medical history, risk factors	X*			
Vital signs 	X*	X		
Physical Examination	X			
CTA	X*	X*  (if collected)		
sPESI	X			
APT Procedure		X		
Echocardiogram 	X*	X  (if collected)	X* (if collected)	X* (if collected)
Quality of life surveys 		X*	X*	X*
Laboratory tests 	X 	X		
Biomarkers 	X*	X		
Adverse/VTE/Bleeding Events		X*	X*	X*
Anticoagulation medications	X	X	X	X

1. Record heart rate, blood pressure, respiratory rate, oxygen saturation vital signs at admission, at start and end of treatment, and once at same time each day of hospitalization  
 2. Includes RV/LV ratio, TAPSE, estimated RVSP, and collapse of the inferior vena cava (IVC) with respiration  
 3. Collect 24 – 48 hours after the start of the APT procedure  
 4. PEmb-QOL and EQ-5D-5L  
 5. Hemoglobin (Hgb), hematocrit (Hct), platelet count, creatinine, activated partial thromboplastin time (aPTT), partial thromboplastin time (PT), and international normalized ratio (INR)  
 6. Record if collected within 48 hours prior to the start of APT procedure  
 7. Troponin, brain natriuretic peptide (BNP)/NT-proBNP, lactate/lactic acid, and D-dimer

## 4. BACKGROUND

---

### 4.1 Pulmonary Embolism (PE)

---

Venous thromboembolism (VTE), comprised of deep vein thrombosis (DVT) and pulmonary embolism (PE), is the third most common cardiovascular disorder in the United States after myocardial infarction and stroke. The 2008 United States Surgeon General's Call to Action to Prevent DVT and PE estimates that 100,000 to 180,000 deaths occur annually from PE in the U.S. alone. In the 2003 U.S. Healthcare Cost and Utilization Project Nationwide Inpatient Sample database, 196,134 VTE-related events, including symptomatic DVT, symptomatic PE, and VTE-related deaths, were calculated to have occurred among acutely ill hospitalized Medical Service subjects, afflicting two out of every 100 of these subjects.

The mortality rate for acute PE exceeds 15% in the first three months after diagnosis, surpassing that of myocardial infarction. In nearly 25% of all subjects presenting with acute PE, the initial presentation is sudden death. The majority of deaths from acute PE results from right ventricular (RV) pressure overload and subsequent RV failure. Survivors of acute PE are at-risk for developing debilitating chronic thromboembolic pulmonary hypertension (CTEPH). Subjects with CTEPH typically experience a "honeymoon" period after acute PE, during which symptoms are absent despite the onset of pulmonary hypertension. Unfortunately, the condition is usually detected when pulmonary hypertension has worsened to the point that it causes dyspnea, hypoxemia, and RV failure.

Therapeutic anticoagulation with immediate parenteral anticoagulants followed by oral agents is the cornerstone of therapy for acute PE. However, while the majority of acute PE subjects has a benign clinical course with standard therapeutic anticoagulation alone, subjects with massive and submassive PE remain at increased risk for adverse clinical events, including RV failure and hemodynamic collapse.

Advanced therapy for patients with acute PE is usually reserved for patients with either massive or submassive PE. Options for advanced therapy include peripherally-administered systemic fibrinolysis, surgical pulmonary embolectomy, catheter-assisted embolectomy, and inferior vena cava (IVC) filter insertion.

Combined ultrasound/fibrinolytic therapy was developed to accelerate thrombolysis and rapidly achieve complete clot lysis while reducing the risk of serious complications such as bleeding. High frequency, low power ultrasound accelerates thrombolysis both in vitro and in vivo. This idea was pioneered by Kudo and confirmed by other investigators. Ultrasound temporarily alters the local architecture of the fibrin clot, thereby enhancing its permeability by reducing the diameter of the fibrin strands and increasing the pore size of the fibrin mesh. Ultrasound energy also provides an acoustic pressure gradient to enable transport of a greater quantity of thrombolytic drug into the clot itself. The resulting faster, more complete clot lysis is due to increased diffusion of the thrombolytic agent into the clot and not mechanical disruption.

EkoSonic® Endovascular System (EKOS) is an FDA cleared and CE Marked drug delivery catheter that uses ultrasound delivered through the catheter core to speed the delivery of

physician-specified fluids, including thrombolytics, into the interstices of the clot and increase the speed of lysis. By making the clot more permeable and pushing the drug into the fibrin mesh, EKOS has the potential to reduce time to lysis, effect more complete lysis, reduce drug dose and, thereby, reduce the risk of bleeding complications.

EKOS Corporation investigated the effectiveness of thrombolytics delivered by ultrasound catheter in acute PE (symptoms  $\leq$  14 days) located in at least one main or proximal lobar pulmonary artery and with a RV/LV of  $\geq 0.9$  on chest CTA or echocardiogram in three prospective, multi-center studies that provide evidence for the efficacy and safety of the Acoustic Pulse Thrombolysis (APT) procedure in the treatment of PE. There are published data for 370 subjects treated with the APT procedure. The studies include one randomized-controlled study ULTIMA involving 30 of 59 patients (pts); and two prospective studies: SEATTLE II involving 150 pts and OPTALYSE PE involving 100 pts.

